# 12.0 Interim Analyses

There are no planned interim analyses for this study.

#### 13.0 Statistical Methods

### 13.1 General Statistical Methodology

All analyses will use SAS version 9.4 or higher.

Unless otherwise noted, continuous variables will be summarized using the number of observations (n), mean, standard deviation (std), median, first quartile (Q1), third quartile (Q3), minimum, and maximum values. The minimum and maximum values will be displayed to the same level of precision as the raw data; the mean, median, Q1, and Q3 values to one additional decimal place and the standard deviation to two additional decimal places.

Categorical variables will be summarized using counts and percentages. Percentages will be rounded to one decimal place, except 100% will be displayed without any decimal places, and percentages will not be displayed for zero counts.

All participants will be used in the analyses as per the analysis populations, using all non-missing data available. No imputation process will be used to estimate missing data.

For the purpose of all safety, and the last assessment prior to the first dose of study IP.

Prior and concomitant medication start/stop date imputation and adverse event start/stop date imputation are described in Appendix-B and Appendix-C, respectively.

AEs will be coded using Medical Dictionary for Regulatory Activities (MedDRA) version 23.1. All TEAEs are defined as an AE with onset after the first dose of IP.

#### 13.2 Participant Analysis Sets

The number and percentage of participants in the FAS, Safety, sets will be provided.

# 13.3 Participant Disposition

The number and percentage of participants screened, screen failed, enrolled in the study will be presented, together with the number and percentage of participants who discontinued from the study prematurely and a breakdown of the corresponding reasons for discontinuation as well as the number and percentage of participants who discontinued early from treatment and corresponding reasons.

Participant disposition will be summarized overall for the Safety analysis set, including the following:

- Number and percent of participants who completed the study
- Number and percent of participants who did not complete the study and reasons for early discontinuation of study

A by-participant disposition listing will be provided. In addition, a separate listing of screening failures with the primary reason for screen failures will be provided.

# 13.4 Eligibility Criteria Violations and Protocol Deviations

Protocol deviations identified during the study will be captured and categorized by the study team review as major and minor deviations on an ongoing basis. In addition, COVID-19 related protocol deviations such as remote telephone/video visit/assessment, home healthcare visit, missed visit/assessment, out of window visit/assessment, safety reporting, investigational product administration, and others will be documented and analyzed as appropriate.

A by-participant listing of all protocol deviations will be provided with columns identifying the following: date of the deviation, type of deviation (Major/Minor), deviation category, and verbatim description.

## 13.5 Demographic and Baseline Characteristics

Demographic and baseline characteristics, such as sex, race, age, height (cm), baseline weight (kg) body mass index (BMI) (kg/m²), and Clinical Dementia Rating (CDR) will be summarized using the Safety analysis set. Data will be summarized using descriptive statistics including sample size (n), mean, std, median, Q1, Q3, minimum, and maximum for continuous variables and numbers and percentages of participants for categorical variables.

Alzheimer's disease history will be summarized and listed by participants.

The baseline for weight, height and BMI is defined as the last non-missing value prior to the first dose of investigational product.

### 13.6 Medical and Surgical History

Medical/surgical history collected at screening will be coded using the Medical Dictionary for Regulatory Activities (MedDRA), Version 23.1. Medical/surgical history data will be summarized by system organ class (SOC) and preferred term (PT). A summary of medical/surgical history that is ongoing at the time of screening will be provided separately. Medical/surgical history will also be listed.

MRI results and amyloid-PET results will be listed by participants.

# 13.7 Physical/Neurological Examinations

A physical examination will be conducted at Screening (Day -21 to Day -8) and baseline (Day -7 and Day -1), as well as Days 14 and ET.

A full physical examination will occur at Screening and will include assessment of body systems (eg, head, eye, ear, nose and throat; heart; lungs; abdomen; and extremities) as well as neurological examination. Thereafter abbreviated physical examinations will include assessment of general appearance, cardiovascular, respiratory, gastrointestinal, and neurological systems, followed by a targeted physical examination as needed.

Clinically significant abnormalities found during Screening or during clinic visits will be reported on the medical history CRF; record clinically significant abnormalities or worsening conditions will be reported on the adverse event CRF, hence will be captured in AE displays. Therefore, no summaries will be provided for physical/neurological examinations.

#### 13.8 Prior and Concomitant Medications

The following analyses will use the Safety Set

All medications taken and procedures undergone during the study will be recorded.

Medications will be presented according to whether they are being taken prior to and/or during the study (concomitant). Prior medications are defined as those taken prior to the initiation of the start of the investigational product, and that ended prior to the IP. Concomitant medications are defined as those with a start date on or after the first dose of investigational product or those with a start date before the first dose of investigational product that is ongoing or with a stop date on or after the first dose of investigational product.

#### 13.9 Treatments

#### 13.9.1 Extent of Investigational Product Exposure and Treatment Adherence

The following analyses will use the Safety Set.

Total drug exposure (in mg) is defined as the total investigational product in mg for SAGE-718 that was taken during the study.

Total exposure duration to investigational product (in days) is defined as Date of last dose – date of first dose + 1. Note that this does not exclude days when the dose has been missed

Percent of the planned exposure received is defined as the total drug exposure, divided by planned exposure, times 100. For participants who complete the treatment period, planned exposure is 14 days of treatment planned times 3 mg. For participants who discontinued the treatment early, the planned exposure is the number of days (last date – first dose date + 1), times 3 mg.

Investigational product adherence (%) is defined as the number of tablets taken, divided by the number of tablets planned to be taken, times 100. The schedule of investigational product is six tablets per day. The number of tablets planned to be taken is defined as follows:

If the participant discontinues treatment within Day 2 and Day 14 (both inclusive), the number of tablets planned to be taken is the last dose day of investigational product × 6.

If the participant does not discontinue treatment, the number of tablets planned to be taken is 84 (6x14).

Investigational product exposure and adherence will be summarized descriptively and listed. The number and percentage of participants with investigational product adherence in categories(<80%, 80-100%, >100%) will be provided. Investigational product accountability will be listed.

All investigational product exposure data will be in by-participant listings, as well as a summary of treatment adherence.

#### 13.10 Visit Windows

The scheduled visits will not be windowed and will be used at a nominal visit value for analysis purposes. The unscheduled and early termination (ET) visit will be mapped to a scheduled visit for analysis. In order to accommodate as much data as possible into analysis, the windows in the table below have been widened compared to protocol-specified operational window, to have no gap between them; these windows are used for analysis purposes only. Once analysis visit windows are assigned, all visits, including scheduled visits, unscheduled visits, and ET visits will be eligible for being flagged as the "analyzed record" within the analysis window; a participant's individual analysis visit window could potentially contain more than 1 visit. In the event of multiple visits falling within an analysis window or in

case of a tie, the following rules will be used in sequence to determine the "analyzed record" for the analysis visit window:

- If the data from the scheduled visit is available, then the scheduled visit data will be used.
- If there is no data from the scheduled visit is available, the data closest to the scheduled study day for that window will be used.
- If there is a tie between the data in the number of days before and after the scheduled day, the later data will be used.

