Abbreviations: CDR = Clinical Dementia Rating Dementia Staging Instrument®; C-SSRS = Columbia—Suicide Severity Rating Scale; d = days; ECG = electrocardiogram; EEG = electrocardiogram; ET = early termination; FSH = follicle stimulating hormone; HIV = human immunodeficiency virus; IP = investigational product;

MRI = magnetic resonance imaging; PET = positron emission tomography;

SAE = serious adverse event; TEAE = treatment-emergent adverse event

Notes: In the event of ET, efforts should be made to collect the Day 14 visit assessments.

When scheduled for the same time point, procedures should be performed in the following order: vital signs, ECG, blood draws, morning meal, IP dosing, then any scheduled postdose and/or

In the setting of public health advisories due to COVID-19, assessments scheduled to be conducted at the study site may be performed via telephone/video if feasible. For assessments that cannot be conducted by phone or video, an in-home visit may be conducted. Information about COVID-19 diagnosis, treatment, and quarantine status will be collected with medical history, AEs, and prior and concomitant medications.

- a Day 4 and Day 21 visits will occur via scheduled telephone calls.
- b Both study partners and participants are to be consented during the Screening Period.
- c In addition to full medical history, all nonpharmacological methods (
 treat or prevent of AD are to be recorded.
- d Vital signs to include temperature, respiratory rate, heart rate, and blood pressure. Heart rate and blood pressure to be collected in supine position and standing position at all scheduled time points (see Section 12.1.4).
- e Full physical examination to be conducted at Screening, abbreviated examinations thereafter (see Section 12.1.3).
- f EEG to be performed for all participants during Screening. If indicated, an unscheduled 1-hour EEG will be performed for that participant (see Section 12.1.6).
- g ECG will be measured after the participant has been in the supine position for at least 5 minutes.
- h "Baseline/Screening" C-SSRS form at Screening and "Since Last Visit" C-SSRS form thereafter.
- i Samples for clinical laboratory assessments, detailed in Table 4, to be collected ≤2 hours prior to dosing during the Treatment Period, and any time of day at other time points. Participants are to be in a fasted state for screening assessments only.
- j Alcohol testing will be performed in the clinic, either by urine dipstick or breathalyzer.

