**Table 1: Visit Windows for Analysis** 

[figure not shown]
Scheduled Visit (+/1 window days) in protocol	Target Study Day	Study Day Window for Visit in Analysis
Day 1	Day 1 (predose)	Day 1 (predose) or last non- missing assessment before pre- dose regardless of scheduled or unscheduled visits
Day 7 (±1 day)	Day 7	Day 2 - Day 10
Day 14 (+1 day)	Day 14	Day 11 - Day 17
Day 28 / last dose + 14 days (±2 day)	Day 28 (last dose date + 14 days)	>= Day 26 (last dose date +12 days)

Note: Parenthesized study day and study day window are for unscheduled visits, EOT and ET for participants who have discontinued treatment prematurely and such visit date is  $\geq 4$  days from the last dose of investigational product intake (ie, visit date – last dose date + 1 > 4).

[figure not shown]
The summary by visit will use the "analyzed records" only – at most one per participant. The data not flagged as the "analyzed record" will be included in listings. An unscheduled visit that does not fall under any analysis window will remain in the database and will be included in the listings.

[figure not shown]

[figure not shown]

[figure not shown]
Sponsor: Sage Therapeutics

[figure not shown]

[figure not shown]

[figure not shown]

Sponsor: Sage Therapeutics

[figure not shown]

[figure not shown]

Sponsor: Sage Therapeutics

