**Table 4 Clinical Laboratory Tests** 

Hematology	Serum Chemistry	Urinalysis	Coagulation
Hematology Red blood cell count Hemoglobin Hematocrit White blood cell count with differential Platelet count Red Blood Cell Indices (MCV, MCH, MCHC) Reflex to Red blood cell morphology if indices are abnormal	Serum Chemistry  Alanine aminotransferase Albumin Alkaline phosphatase Aspartate aminotransferase Total bilirubin Direct bilirubin Indirect bilirubin Total protein Creatinine Blood urea nitrogen Creatine kinase Gamma-glutamyl transferase	Urinalysis pH  Protein Glucose Red blood cell Nitrite Leukocyte esterase Ketones Bilirubin Urobilinogen	Coagulation  Activated partial Thromboplastin time Prothrombin time International normalized ratio
apnormai		Urobilinogen	
	Thyroid stimulating hormone (TSH)		

If a normal range is provided for the parameter, out-of-range values will be flagged as low or high, where applicable, in the participant data listings

The number and percentage of participants with potentially clinically significant (PCS) values will be provided in separate displays in hematology, serum chemistry, and liver function tests provided for such occurrence by time point.

PCS values will be identified for specific laboratory parameters as outlined in Table 5.

Liver function tests will be monitored closely for PCS values, and will be summarized for occurrence any time post-baseline for the following parameters for these PCS thresholds (for conditions involving more than one parameter, the results need to be from the same timepoint):

Alanine Aminotransferase: >3xULN, >5xULN, >10xULN Aspartate Aminotransferase: >3xULN, >5xULN, >10xULN

Alanine Aminotransferase or Aspartate Aminotransferase: >3xULN, >5xULN, >10xULN

Alkaline Phosphatase: >1.5xULN, >2xULN

Total Bilirubin: >1.5xULN, >2xULN

Total Bilirubin > 2xULN **AND** (Alanine Aminotransferase or Aspartate Aminotransferase >3xULN)
Total Bilirubin >2xULN **AND** Alkaline Phosphatase >2xULN **AND** (Alanine Aminotransferase or

Aspartate Aminotransferase >3xULN)

Any lab results considered clinically significant by the investigator will be captured as adverse events, hence will show up in AE displays.

Pregnancy test results will be listed but not summarized.

Table 5 Potentially Clinically Significant Values for Specific Laboratory Parameters

Laboratory Parameter	Gender	Units	Criteria for PCS Values (Observed values)		
			High	Low	
Hematology					
Hemoglobin	Male	g/L	>185	<115	
	Female	g/L	>170	<100	

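### An on-drug early-termination visit after the scheduled Day 7 visit and by Day 10 is left out of the by-visit safety summaries

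*SAP*

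**What the plan says.** SAP 13.10 treats the two kinds of visit differently. For planned visits, "The scheduled visits will not be windowed and will be used at a nominal visit value for analysis purposes". For the others, "The unscheduled and early termination (ET) visit will be mapped to a scheduled visit for analysis". SAP Table 1 gives Day 7 the window Day 2 to Day 10 and Day 14 the window Day 11 to Day 17.

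When a window holds more than one visit, the first selection rule is "If the data from the scheduled visit is available, then the scheduled visit data will be used". Closeness to the target day, and then the later date, count only when there are no scheduled data. By-visit summaries use the selected record, "at most one per participant"; the other records are listed.

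The note to Table 1 gives an alternative window, counted from the last dose, to premature discontinuers. It applies only when the visit is 4 or more days after that dose.

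The protocol's Schedule of Assessments (Table 2) puts ET in the same column as Day 14, and its notes add: "In the event of ET, efforts should be made to collect the Day 14 visit assessments". Under Protocol 8.4.1, participants who stop drug are invited to attend the scheduled visits through Day 14. Only those who decline are asked to have an ET visit.

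**The concern.** Whether a termination assessment enters the by-visit tables depends on the calendar day on which it happens. An ET visit before any scheduled Day 7 visit is used as Day 7. An ET visit on Days 11 to 13 is used as Day 14. An on-drug ET visit after the Day 7 visit and up to Day 10 is used in neither row. The participant is represented by the earlier Day 7 values and contributes nothing to Day 14. SAP 13.10 gives no reason for this difference, and its stated aim in widening the windows is to bring in as much data as possible.

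The affected summaries carry the secondary endpoint: change from baseline in vital signs, laboratory analytes, ECG and C-SSRS responses. In a single-arm safety study of about 22 people, the last on-drug assessment of someone who stopped is among the more informative records. For C-SSRS, the form completed at ET covers the interval since the Day 7 visit, yet the by-visit row would show the Day 7 answer.

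**Working it through.** **Plan's own figure.** SAP 10.2 and Protocol 13.8 plan about 22 participants to obtain 20 completers at 10% dropout. 20 × 1.10 = 22 gives the stated number; 20 / 0.90 = 22.2 is close to it. Expected dropouts are 22 × 0.10 = 2.2, or about 2.

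**Which ET days are displaced.** Inputs are the Table 1 windows, the first selection rule in 13.10, and the Day 7 ± 1 day visit allowance. The ET visit is taken to be within 3 days of the last dose, so the alternative window does not apply.

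| Scheduled Day 7 visit held on | ET days displaced | ET days used as Day 14 |
|---|---|---|
| Day 6 | 7, 8, 9, 10 | 11–13 |
| Day 7 | 8, 9, 10 | 11–13 |
| Day 8 | 9, 10 | 11–13 |

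This assumes the scheduled visit has data for the parameter. If it does not, the ET value is used.

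**Chance of at least one displaced record.** Assume 2 dropouts, each with an attended on-drug ET visit, and ET days spread evenly over the 12 days from Day 2 to Day 13. With *a* displaced days, P = 1 − (1 − a/12)².

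- Visit on Day 8, a = 2: 1 − (10/12)² = 0.31; expected number 2 × 2/12 = 0.33.
- Visit on Day 7, a = 3: 1 − (9/12)² = 0.44; expected number 2 × 3/12 = 0.50.
- Visit on Day 6, a = 4: 1 − (8/12)² = 0.56; expected number 2 × 4/12 = 0.67.

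If each dropout has only a 50% chance of having such a visit (an assumption), a = 3 gives 1 − (1 − 0.5 × 3/12)² = 0.23.

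One displaced record is 1/22 = 4.5% of the planned participants, but half of the discontinuers if there are 2.

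**Which outputs are affected.**

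- Left out: by-visit change from baseline for laboratory values (SAP 16.2), vital signs (16.4) and ECG (16.5); the by-visit C-SSRS summary (16.6); ECG interpretation counts by time point (16.5, Table 14.3.5.2); and hematology PCS counts, whose Table 14.3.3.1.2 is titled as by time point.
- Ambiguous: chemistry PCS counts. The text of 16.2 has "provided for such occurrence by time point", but the title of Table 14.3.3.2.2 does not mention time point.
- Should still include the record: any-time post-baseline counts for vital signs and QTcF (PCS values and changes), liver-test thresholds and C-SSRS categories. The SAP restricts only the by-visit summaries to selected records, but does not state that these counts use the rest.
- Retain the finding in any case: the listings, and the adverse event tables if the finding is judged clinically significant.

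The visible table list in SAP Appendix F shows no separate ET or last on-treatment table.

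**The case against.** The strongest reply is that preferring the scheduled record is a legitimate prespecified rule, that few records are at risk, and that the plan already has safeguards. Much of this stands. The primary endpoint, incidence of treatment-emergent adverse events, does not depend on visit windows. Events leading to discontinuation of drug or study have their own tables. The shared Day 14 and ET column governs what is collected and does not by itself bind the analysis.

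Three stronger readings are tempting, and the documents do not support them.

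- A reader might infer that the Day 14 rows describe only people who tolerated drug beyond Day 10. Protocol 8.4.1 lets participants who stopped drug continue to Day 14, and those scheduled visits enter at their nominal visit. Nor does an ET visit imply a safety problem, since withdrawal may be at the participant's request or for compliance or administrative reasons.
- A reader might infer that an abnormal ET value would not be summarized anywhere. A systolic rise of 30 mmHg, for example, meets the change criterion of 30 or more in SAP Table 6, which is counted at any time post-baseline. It would be missing from the by-visit mean and maximum.
- A reader might infer that all laboratory PCS counts lose the record. Liver thresholds are counted at any time post-baseline, and the chemistry wording is ambiguous. Only the hematology loss is clear.

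What the reply leaves standing is the by-visit omission itself, and the lack of a statement that any-time counts use unselected records.

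**Conclusion.** The point holds for by-visit and by-time-point summaries. An ET record within 3 days of the last dose, after an attended scheduled Day 7 visit and no later than Day 10, is displaced from them by rule. The expected number is below one participant, with a 31% to 56% chance of at least one under the stated assumptions. That range treats every dropout as having an attended on-drug ET visit, so it is towards the upper end. Continued attendance to Day 14, loss to follow-up, or a visit 4 or more days after the last dose would all lower it.

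The effect is confined to how the secondary safety endpoint is displayed. It is worth correcting because the record omitted belongs to someone who left early and because the correction uses data already collected.

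**What to change.** In SAP 13.10 and the table specifications, add a row for the last on-treatment value, defined as the last scheduled, unscheduled or ET record within 3 days of the last dose. Put it in the change-from-baseline tables and in the by-time-point PCS and ECG tables. State that all any-time post-baseline counts, including C-SSRS, use every post-baseline record whether or not it was selected for a window. Align the chemistry PCS text in 16.2 with the title of Table 14.3.3.2.2.

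An alternative is a narrow remapping. Only when an on-drug ET record in the Day 2 to Day 10 window is displaced by an attended scheduled Day 7 record, summarize it in a row labelled *Day 14 or ET* and show how many ET records that row contains. All other mappings stay as they are. A broader rule sending each ET record to the next unattended visit should be avoided: after a missed Day 7 visit, it would move an ET on Days 11 to 13 out of the Day 14 window and into the Day 7 row.

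The cost is SAP wording and programming, with no new data collection: one extra row per table, or a row that mixes about 7 to 14 days of exposure.
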